7.3. Vital Signs and Physical Examination Findings

7.3.1. Definitions

The following vital signs parameters will be analyzed.

- Pulse (bpm)
- Systolic blood pressure, SBP (mmHg)
- Diastolic blood pressure, DBP (mmHg)

A listing of subjects with treatment-emergent clinically important vital signs will be presented, along with a listing of all vital sign measurements.

Table 5: Pulse, SBP and DBP are classified in the following abnormality codes.

	Pulse	DBP ^a	SBP ^a
Abnormality Code	(bpm)	(mmHg)	(mmHg)
Abnormally low	≤50	≤50	≤90
Grade 1 or mild	-	>90 - <100	>140 - <160
Grade 2 or moderate	-	≥100 - <110	≥ 160 - <180
Grade 3 or severe	-	≥110	≥180
Abnormally high	≥120	-	-

Classification of adverse events related to hypotension/hypertension should be done according to the DAIDS grading table (Appendix 7 at protocol).

In determining abnormalities, the following rules are applied:

- worst grades/abnormalities are determined over the whole observational period for each trial period separately, including post-reference scheduled *and* unscheduled measurements of that phase.
- The abnormalities 'abnormally low' and 'abnormally high'/grades are considered equally important, i.e. if a subject has as well an abnormally low as an abnormally high or graded value post-reference, both abnormalities are shown in the tables. (This means that the sum of the percentages can be more than 100%).

Definition treatment-emergent:

An abnormality will be considered treatment-emergent in a particular period if it is worse than the reference corresponding to this period. If the reference is missing, the abnormality is always considered as treatment-emergent. A shift from 'abnormally low' at reference to 'abnormally high' or 'grade' post reference (or vice versa) is also treatment-emergent.

7.3.2. Analysis Methods

Continuous vital sign parameters including height, weight, pulse, blood pressure (systolic and diastolic), and Body Mass Index (BMI) will be summarized at each assessment time point by descriptive statistics (mean, standard deviation, median, minimum and maximum) per treatment arm.

Cross-tabulations for the worst abnormalities versus reference per vital signs test will be produced by treatment arm.

Descriptive statistics for the actual values and changes from baseline (including BMI, weight) per timepoint will be presented. The only reference time point that will be used to calculate these changes is the timepoint closest to the first drug intake after randomization.

BMI will be calculated as weight (kg)/(height (m²)), at each time point that body weight is measured. The height measurement collected at screening will be used in the calculation. The frequency tabulations will be presented for BMI as a categorical variable and the descriptive statistics will be summarized for BMI as a continuous variable.

Physical examination findings and changes from baseline at each scheduled time point will be tabulated per treatment arm. Abnormal physical examination findings will also be listed.

8. PATIENT REPORTED OUTCOMES (PROs)

8.1. PROs

Following PROs will be assessed at the time points indicated in the Schedule of Activities (SoA). Appendix 8 in the Protocol provided all information of PROs questionnaires. Participants will complete the PROs using the sponsor-provided electronic devices.

8.1.1. HIV-SI

The HIV-Symptom Index (HIV-SI) is a validated PRO instrument that assesses the burden of 20 common symptoms associated with HIV treatment or disease.⁵ Respondents are asked about their experience with each of 20 symptoms during the past 4 weeks using a 5-point, Likert-type scale. Response options and scores are as follows: (0) "I don't have this symptom;" (1) "I have this symptom and it doesn't bother me;" (2) "I have this symptom and it bothers me a little;" (3) "I have this symptom and it bothers me;" (4) "I have this symptom and it bothers me a lot." The 20 symptoms comprising the HIV-SI are fatigue/loss of energy, difficulty sleeping, nervous/anxious, diarrhea/loose bowels, changes in body composition, feeling sad/down/depressed, bloating/pain/gas in stomach, muscle aches/joint pain, problems with sex, trouble remembering, headaches, pain/numbness/tingling in hands/feet. skin problems/rash/itching, cough/trouble breathing, fever/chills/sweats. dizzy/lightheadedness, body weight loss/wasting, nausea/vomiting, hair loss/changes, and loss of appetite/food taste. Symptoms scores can be dichotomized into not bothersome (scores of 0 or 1) or bothersome (scores of 2, 3 and 4) and overall bothersome symptom count at baseline can be generated by counting the number of individual symptoms scored as bothersome.⁶

8.1.2. BSQ-8D

The Body Shape Questionnaire (BSQ-8D) is an 8-item version of the 34-item self-report questionnaire

that was developed and validated to measure concerns about body shape; in particular, it focused on the phenomenal experience of "feeling fat".^{7, 8} Respondents are asked about how they have been feeling about their appearances over the past four weeks. Each item from this questionnaire is answered using a 6-point Likert scale: 1 (never), 2 (rarely), 3 (sometimes), 4 (often), 5 (very often), and 6 (always) and the overall score is the total across the 8 items.

8.1.3. DAILY EATS

The DAILY EATS will be administered to measure eating-related concepts such as hunger, appetite, cravings, and satiety. The home-based DAILY EATS should be completed daily, preferably in the evening, and, whenever possible, in the same setting for 7 consecutive days. The site should contact participants approximately 7 days prior to the Baseline (Day 1), Week 24 and Week 48 visits, preferably by telephone, to remind the completion of the DAILY EATS for 7 consecutive days prior to the applicable visit. For participants who discontinue early from study intervention, no DAILY EATS completion is required at the ESID visit.

8.1.4. PGIC and PGIC-S

The Patient Global Impression of Change (PGIC) is a global index that is used to rate the overall status of the participant related to the participant's condition. It is rated by the participant and is based on the single question, "Compared to before starting the study or compared to the Week 24 visit, my overall status is, where 1=very much improved, 2=somewhat improved, 3=a little improved, 4=no change, 5=a little worse, 6=somewhat worse, and 7=very much worse."

The single-item PGIC for satiety (PGIC-S), with question, "Compared to before starting the study or compared to the Week 24 visit, how would you rate your satisfaction (fullness) after meals in the past 7 days?" and where 1=much more satisfied, 2=moderately more satisfied, 3=a little more satisfied, 4=no change, 5=a little less satisfied, 6=moderately less satisfied, and 7=much less satisfied, will also be used. The content validity of the PGIC-S has been demonstrated in overweight and obese patients with and without T2DM, although the psychometric properties of the PGIC-S were not evaluated.

8.2. PRO Analysis Methods

Descriptive statistics for absolute values, including total scores, will be calculated for each PRO measure including HIV-SI, BSQ-8D, DAILY EATS, PGIC (PGIC-S) at each timepoint.

The changes from baseline in the proportion of participants who have bothersome symptoms (scores of 2, 3 or 4) across all items of the HIV-SI at Weeks 24 and 48 will be summarized by treatment arm; the changes from baseline in the proportion of participants who have any symptoms (scores of 1, 2, 3 or 4) across all items of the HIV-SI at Weeks 24 and 48 will be summarized by treatment arm.

The changes from baseline in the scores on the BSQ-8D and proportion of participants who have no concern (<19), mild concern (19-25), moderate concern (26-33) or marked concern (>33) with their body shape at Weeks 24 and 48 will be summarized.

The changes from baseline in the scores on the DAILY EATS at Weeks 24 and 48 will be summarized. Further, descriptive statistics will be presented for item-level weekly scores on the DAILY EATS, item-level weekly change scores on the DAILY EATS, Eating Drivers Index (EDI) weekly scores, and EDI

weekly change scores, respectively. Item-level weekly scores are computed as the average of the non-missing item-level scores over the 7-day (weekly) diary period. EDI is computed as the average of the item-level weekly scores for Worst Hunger (Item 2), Appetite (Item 3), and Cravings (Item 4).

Change in the proportion of participants who have bothersome symptoms (scores of 2, 3 or 4) across all items of the HIV-SI from Baseline to Week 24 (Immediate Switch Arm) compared to the Change in the proportion of participants who have bothersome symptoms (scores of 2, 3 or 4) across all items of the HIV-SI from Week 24 to Week 48 (Delayed Switch Arm will be summarized descriptively.

Change in the proportion of participants who have any symptoms (scores of 1, 2, 3 or 4) across all items of the HIV-SI from Baseline to Week 24 (Immediate Switch Arm) compared to the change in the proportion of participants who have any symptoms (scores of 1, 2, 3 or 4) across all items of the HIV-SI from Week 24 to Week 48 (Delayed Switch Arm) will be presented

Descriptive statistics for PGIC and PGIC-S at Week 24 (Immediate Switch Arm) and PGIC and PGIC-S at Week 48 (Delayed Switch Arm) will be calculated.

Association between treatment arm and each bothersome symptoms of the HIV-SI adjusting for baseline variables at Weeks 24 will be calculated. For each symptom we can consider using stepwise variable selection criterion to choose statistically significant covariates at baseline. To understand meaningful change in scores on PRO measures, PGIC-S will be used as an anchor to determine meaningful change scores for the DAILY EATS in participants living with HIV.

Association of the specific item of the HIV-SI with body weight loss/wasting at Weeks 24 and 48 will be evaluated. Association between BSQ-8D scores and percent change in body weight and/or >5% in change in weight will be presented.

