9.4.5. Patient-reported Outcomes Analyses

Descriptive statistics for absolute values will be calculated for each PRO measure including BSQ-8D, HIV-SI, DAILY EATS, and PGIC and at each timepoint per Schedule of Activities (SoA). In addition, changes from baseline in the proportion of participants who have bothersome symptoms (scores of 2, 3 or 4) across all items of the HIV-SI at Weeks 24 and 48, changes from baseline in the proportion of participants who have any symptoms (scores of 1, 2, 3 or 4) across all items of the HIV-SI at Weeks 24 and 48, and changes from baseline in the scores on the BSQ-8D and proportion of participants who have no concern (<19), mild concern (19-25), moderate concern (26-33) or marked concern (>33) with their body shape at Weeks 24 and 48 and changes from baseline in the scores on the DAILY EATS at Weeks 24 and 48 will be summarized. Association between treatment arm and each bothersome symptom of the HIV-SI adjusting for baseline variables at Weeks 24 will be calculated. To understand meaningful change in scores on PRO measures, PGIC-S will be used as an anchor to assess meaningful change scores for the DAILY EATS in participants living with HIV.

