5.2.3. Analysis Methods

The statistical hypothesis is the following:

 H_0 : Dt-Dc=0 versus H_1 : Dt -Dc \neq 0.

Where H₀ is the null hypothesis, H₁ is the alternative hypothesis; Dt= percent change in body weight at Week 24 from Baseline for D/C/F/TAFFDC (Immediate Switch Arm), Dc = percent change in body weight at Week 24 from Baseline for active control (Delayed Switch Arm).

The statistical hypothesis will be tested using mixed model for repeated measures (MMRM) below.

Y = Baseline BMI + Sex + Race + Time + Treatment + Treatment*Time + Subject + E

In this model, Y is the %change in body weight from baseline at time week 4, week 12, and week 24; baseline BMI, sex, race, time, treatment and treatment*time are fixed effects; subject is a random effect; and E is the random error. Subject is treated as a random effect to incorporate the variability and correlation among repeated measures (time).

The statistical hypothesis will be tested by estimating the treatment LSmeans for the %change in body weight corresponding to the time measurement at week 24. The significance level p-value and 95% confidence interval for the difference will be provided.

To control for the overall Type I error rate at the 2-sided 0.05 significance level, the weighted inverse-normal p-value combination test will be used to combine p-values from interim stage and primary analysis stage⁴. The overall p value will be calculated by the combination statistic below

$$Z(p_1,\,p_2) = \text{w1}\ \Phi^{-1}(1 - p_1) + \text{w2}\ \Phi^{-1}(1 - p_2)$$

where $w_1=\sqrt{(n_1/N)}$, $w_2=\sqrt{(n_2/N)}$, n_1 and n_2 are number of subjects in IA stage and remaining primary stage.

All available data from randomized participants that have received at least one dose is included (ITT analysis set) will be used for the analysis, regardless of the occurrence of intercurrent events.

Missing Data for body weight is assumed as Missing At Random (MAR). In addition, as a sensitivity analysis, a control-based multiple imputation will be applied to the MMRM model, assuming weight data is not missing at random.

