
Efficacy:

- Proportion of participants with confirmed virologic rebound through Week 24 and Week 48, respectively.
- Proportion of participants with virologic response (HIV-1 RNA<50 copies/mL) at Week 24 and Week 48, respectively, according to the FDA snapshot algorithm
- Proportion of participants with virologic failure (HIV-1 RNA ≥50 copies/mL) at Week 24 and Week 48, respectively, according to the FDA snapshot algorithm
- Proportion of participants having virologic response (HIV-1 RNA<200 copies/mL) at Week 24 and Week 48, respectively, according to the FDA snapshot algorithm
- Proportion of participants having virologic failure (HIV-1 RNA ≥200 copies/mL) at Week 24 and Week 48, respectively, according to the FDA snapshot algorithm
- Change from Baseline in CD4+ cell count at Week 24 and Week 48 respectively.

Resistance:

- Proportion of participants with baseline DRV, FTC, TFV and INI resistance-associated mutations (RAMs) based on historical genotypes.
- Incidence of observed genotypic and phenotypic ARV resistance for participants meeting HIV-1 RNA rebound criteria through Weeks 24 and 48, respectively.
- Proportion of participants with newly identified post-baseline RAMs and phenotypic resistance compared to pre-baseline resistance tests when available, upon meeting confirmed virologic rebound through Weeks 24 and 48, respectively.

PROs:

- Change from Baseline in the proportion of participants who have bothersome symptoms (scores of 2, 3 or 4) across all items of the HIV-SI at Week 24 and Week 48, respectively.
- Change from Baseline in the proportion of participants who have any symptoms (scores of 1, 2, 3 or 4) across all items of the HIV-SI at Week 24 and Week 48, respectively.
- Association between treatment arm and each bothersome symptom of the HIV-SI adjusting for Baseline variables at Week 24 and Week 48, respectively.
- PGIC and PGIC-S at Week 24 and Week 48, respectively.

Adherence:

• Adherence rates by participant self-report using 4-day recall at Weeks 4, 12, 24, 36 and 48, respectively.

Exploratory:

Exploratory clinical biomarker:

• Change from Baseline in alpha melanocyte-stimulating hormone at Week 24 and Week 48, respectively.

Exploratory PROs:

- Change from Baseline in the scores on the DAILY EATS at Week 24 and Week 48, respectively.
- Change from Baseline in the scores on the BSQ-8D at Week 24 and Week 48, respectively.

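### SAP 8.2 leaves open stepwise covariate selection, symptom by symptom, for the arm association with the 20 HIV-SI items, and nothing else in the plan fixes the covariates

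*SAP*

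**What the plan says.** SAP section 8.2 sets the analysis: "Association between treatment arm and each bothersome symptoms of the HIV-SI adjusting for baseline variables at Weeks 24 will be calculated". It continues: "For each symptom we can consider using stepwise variable selection criterion to choose statistically significant covariates at baseline". SAP section 8.1.1 says that the instrument "assesses the burden of 20 common symptoms associated with HIV treatment or disease" and allows each item to be split into not bothersome (0 or 1) and bothersome (2 to 4). This is therefore up to 20 separate binary analyses.

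The other places that mention the analysis add no covariates. Protocol section 9.4.5 has: "Association between treatment arm and each bothersome symptom of the HIV-SI adjusting for baseline variables at Weeks 24 will be calculated". The endpoint list in SAP section 6.2.1 has: "Association between treatment arm and each bothersome symptom of the HIV-SI adjusting for Baseline variables at Week 24 and Week 48, respectively". Neither document gives a candidate list, entry or removal thresholds, the regression model, whether arm is forced in, or a multiplicity approach for these 20 results.

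The primary model in SAP section 5.2.3, by contrast, is written out: "Y = Baseline BMI + Sex + Race + Time + Treatment + Treatment*Time + Subject + E".

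**The concern.** Per-symptom stepwise selection is the only covariate method that the plan names for a listed secondary endpoint. Three things follow if it is used.

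- Each item may be adjusted for a different set, chosen partly by chance. If the model is logistic, odds ratios conditional on different covariates are not on the same scale, so a table of 20 arm effects is hard to read across.
- Ordinary intervals and p-values treat the chosen set as if it had been fixed in advance.
- The baseline status of the same symptom is collected (the Schedule of Activities has HIV-SI at Day 1), but it enters only if it passes the significance screen.

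The optional wording also leaves open whether to select at all. The trial is open-label, so that choice can be made by people who know the arms. At stake is the credibility of one secondary patient-reported analysis.

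**Working it through.** **The plan's own figure.** The documents give no power or alpha for the HIV-SI association. The sample size behind it is the primary one: 16/ES² = 16/0.54² = 54.9, so 55 per arm and 110 in total, as stated in protocol section 9.2 and SAP section 1.5.

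**Assumptions not in the documents.** 10, 20 or 30 candidate covariates; entry at p<0.05; symptom prevalence as shown below. SAP Tables 3 and 4 list more than 40 baseline rows, some overlapping, so 10 is not a high guess. The SAP does not say, however, that those rows are the candidates.

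**Spurious covariates.** With k unrelated candidates, the expected number of false entries per model is 0.05k, and the chance of at least one is 1 − 0.95^k.

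- k = 10: 0.5 expected; 1 − 0.95^10 = 40%; over 20 items, 0.40 × 20 = about 8 models.
- k = 20: 1.0 expected; 64%.
- k = 30: 1.5 expected; 79%.

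**Events.** At an assumed 20% prevalence, 0.20 × 110 = 22 events per item, or 22/10 = 2.2 per candidate with 10 candidates. At the maximum sample size of 150 this is 30 events, or 3.0 per candidate.

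**Effect on the arm estimate.** Simulation settings: 110 participants, 55 per arm, no arm effect, 20 symptoms that all share one true predictor (log odds ratio 0.5 per SD), independent covariates, forward selection with arm forced in, and 1,200 fits per row. The comparator is a fixed model holding that one true predictor, which is the best case for a fixed model.

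| Candidates | Prevalence | Distinct sets among 20 | Mean covariates selected | Type I error, fixed | Type I error, stepwise | SD of arm log OR, fixed to stepwise |
|---|---|---|---|---|---|---|
| 10 | 15% | 9.3 | 0.98 | 4.7% | 5.1% | 0.60 to 0.63 |
| 10 | 30% | 8.6 | 1.13 | 5.5% | 5.8% | 0.45 to 0.47 |
| 20 | 15% | 14.3 | 1.58 | 4.0% | 6.2% | 0.57 to 0.70 |
| 20 | 30% | 14.0 | 1.65 | 4.3% | 6.2% | 0.44 to 0.49 |
| 30 | 15% | 17.4 | 2.26 | 4.6% | 7.5% | 0.58 to 0.82 |
| 30 | 30% | 17.2 | 2.29 | 5.2% | 7.0% | 0.43 to 0.51 |

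The Monte Carlo standard error of a 5% rate is √(0.05 × 0.95/1,200) = 0.6 percentage points. The 10-candidate rows therefore show no clear inflation; the 30-candidate rows do.

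**Is a real predictor kept?** Roughly, with 10 candidates at 15% prevalence, mean selected minus expected false entries is 0.98 − 9 × 0.05 = 0.53. The one true predictor entered only about half the models. A stronger predictor would be kept more often, but selection does not guarantee it.

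**Multiplicity is separate.** Twenty independent tests at 0.05 give 1 − 0.95^20 = 64% family-wise error, whether or not the covariates are fixed.

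**The case against.** The strongest reply is that the SAP only says stepwise selection can be considered, that arm is randomised so an unrelated covariate does not confound it, and that this is a secondary analysis with no alpha attached. SAP section 8.2 also summarises the change in bothersome-symptom proportions by arm with no covariate selection, so an unaffected by-arm result will exist. All of this is right, and it limits the size of the point. It does not close the gap, because the option covers both whether to select and what is selected, and no section settles either.

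A reader might infer more than the documents support:

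- *That 20 differently adjusted analyses are planned.* The text states an option, and the simulation gives about 9 to 17 distinct sets, not 20.
- *That the arm effects would be badly overfitted.* With 10 candidates, type I error is 5.1 to 5.8% and the SD of the arm estimate rises by 0.02 to 0.03. Larger effects need a longer candidate list.
- *That events per item are known to be few.* No HIV-SI prevalence appears in either document; every event count here is hypothetical.
- *That the baseline status of the symptom is the only covariate that matters.* Nothing in the documents says so. If it is strongly prognostic, stepwise selection would usually keep it.

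It is also fair that a fixed model does not cure sparse data. Arm, baseline item, sex and race are four slopes; with 22 events that is 22/4 = 5.5 events per slope.

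**Conclusion.** The point holds as a prespecification gap with a poor method left open as the way to fill it. If stepwise selection were used at 110 participants, adjustment sets would differ across many items (about 9 distinct among 20 with 10 candidates, about 17 with 30), intervals would ignore the selection, and the item's own baseline status would not be assured. The cost to the arm comparison is modest: type I error of about 5 to 6% with 10 candidates, up to about 7.5% with 30, and an estimate that is slightly to clearly less stable. These sizes rest on assumed candidate numbers, prevalence and independent covariates; with a short candidate list they would be small. The primary weight analysis has its own fixed model and is not affected.

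**What to change.** Delete the stepwise sentence in SAP section 8.2 and replace it with:

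- one logistic model for every item at Week 24, with arm forced in, baseline bothersome status of that item, sex and race (the stratification factors), and no variable selection;
- for items with too few events, by a count set in advance, a penalised (Firth) fit or counts by arm only;
- a statement that the 20 results are descriptive, with no multiplicity control.

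In the same edit, reconcile the time points. SAP section 6.2.1 lists this arm association at Week 48 as well, yet the opening of that section restricts Week 48 endpoints to the Immediate Switch Arm, and SAP section 8.2 and protocol section 9.4.5 name Week 24 only.

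The cost is a few lines of SAP text. All inputs are already collected, and one common model is simpler to program than 20 selected ones. The downside is that items with few events may still give imprecise estimates.
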